Early Intervention to Reduce Alcohol Misuse and Abuse in the Ohio Army National Guard
(Project GUARD)

Protocol

Version Date: 02/18/2019

NCT Number: NCT02860442

Objectives

The proposed project, Project GUARD, is a fully-powered randomized controlled trial of a smartphone app which includes an alcohol brief intervention (SP-BI) versus an Enhanced Usual Care (EUC) condition for National Guard members in the State of Ohio who meet criteria for at-risk drinking in the previous 4 months.

The specific aims are to compare SP-BI and EUC in:

1. Reducing the frequency and intensity of at-risk drinking at 4-, 8- and 12-months;
2. Decreasing binge drinking at 4-, 8- and 12 months.

The secondary aims are to:

1. Compare the SP-BI and EUC conditions in reducing the frequency of illicit drug use and depressive symptoms at 4-, 8- and 12-months;
2. Examine if deployment status moderates the effect of intervention assignment (SP-BI or EUC) on post-intervention drinking, depressed feelings, and other substance use.

Design

After tailoring the content of the SP-BI intervention for NG soldiers, the proposed study will screen ~3,100 individuals over the three year enrollment period to identify 750 participants with at-risk drinking across the 2 sites. Participants in this study will be randomized to either the SP-BI (n=375) or the EUC condition (n=375) and followed at 4, 8 and 12 months post-enrollment. The study is intended to address the primary and secondary aims and corresponding hypotheses listed below.

Methods

Participants who are randomized to the SP-BI condition will receive an informational brochure with resources available to members of the military related to mental health and alcohol use and will download a free app on to their smartphones. The app will be developed to be used on both Android and iPhone platforms and will be used over 12 weeks to deliver the study intervention. They will be contacted to complete 4-, 8-, and 12-month follow-up assessments.

Those assigned to the control condition will receive an informational brochure with resources available to members of the military related to mental health and alcohol use. They will be contacted to complete 4-, 8-, and 12-month follow-up assessments.

Randomization:

After the baseline assessment is completed, participants will be assigned to one of the two study conditions (SP-BI or EUC) using a computerized randomization system. Random assignment will be stratified based on gender and an AUDIT- \geq score > 19 .

Intervention

Brief Intervention

Smart Phone (SP-BI) Content. Participants in the SP-BI condition will receive a 20-30 minute intervention session through an app program. The intervention will be based on the FRAMES

format: providing personalized Feedback (regarding substance use, risk factors), emphasis on Responsibility for change, Advice, Menu of options, Empathic clinical behaviors, and support of Self-efficacy regarding making changes. The intervention is designed to address the primary target behavior of alcohol use, and will include a tailored review of participants' goals/values, feedback regarding their present alcohol use patterns and consequences (either actual experiences or potential based on risk behaviors), developing a discrepancy between their alcohol use and ability to meet goals and values through a decisional balance exercise, and formulation of a "change plan" tailored for each participant.

Measures

Background Characteristics. The Substance Abuse Outcomes Module (SAOM) will be used to measure background characteristics including basic demographics (i.e., gender, age, race, ethnicity, marital status) and other background variables (e.g., education, employment, income, legal history). The SAOM has undergone extensive reliability and validity examinations (Smith et al., 2006).

Alcohol Use. As recommended by (Babor, 2007; Babor & Hall, 2007; Babor et al, 2007) and the IOM Report (Institute of Medicine, 2012) we will administer the full AUDIT which includes the AUDIT-C (Bush et al., 1998; Saunders et al., 1993) assessing alcohol consumption using 3-items: average quantity, average alcohol use frequency, and binge drinking (5 or more drinks/day for men; 4 or more drinks/day for women) over the past 4-months, and the 7 consequence questions. In addition to the standard item responses (which are categorical groupings such as 5-6 drinks), we will probe for exact numbers. Thus, for data analyses purposes, we will assess these alcohol consumption variables using counts and continuous response scales. Recent literature, including a review paper (Reinert & Allen, 2007) and population-based study (Dawson et al., 2005a, 2005b) support the internal consistency, test-retest reliability, and accuracy of the AUDIT-C in identifying at-risk alcohol use (hazardous use).

Revised Injury Behavior Checklist (RIBC). The original injury behavior checklist was developed for adolescent (Starfield, 1991) and revised for adults (Longabaugh et al., 2001). Participants indicate in the past year how often each of 18 injuries occurred, if they were treated by a doctor for the injury, and if alcohol was consumed within 2 hours of the injury. Prior research demonstrates the RIBC is related to outcomes following a brief intervention (Longabaugh et al., 2001). The RIBC has been modified to include two collapsed questions for intentional and unintentional injury.

Other Drug Use. The Alcohol, Smoking, and Substance Involvement Screening Test (ASSIST 3.0) is an 6-item questionnaire developed as a brief screen for at-risk use of psychoactive substances (WHO Assist Working Group, 2002) including: tobacco, alcohol, cannabis, cocaine, amphetamine-type stimulants, sedatives, hallucinogens, inhalants, opioids, and other drugs. We will use the item that measures how often each substance was used in the past 4 months.

Depressive Symptoms. The PHQ-9 (Kroenke et al., 2001) will further assess symptoms of depression; it has 94% specificity and 99% sensitivity for current major depressive disorder. The total score ranges from 0-27, with severity defined as: none (0-5), mild (6-10), moderate (11-15), major (16-20), severe (21+). Recent suicidal ideation will be assessed with one question: "Have

you thought that you would be better off dead or that you wanted to hurt yourself in some way?" from the PHQ-9, and the four additional questions, "Did you have a period of time where you thought about death a lot?", "Did you feel so low you thought a lot about committing suicide?", "Did you make a plan as how you might do it?", "Did you attempt suicide?" A positive response to any of these question will create a "flag" in the computer that will prompt staff (regardless of study condition) to implement a protocol for further assessment for harm to self.

Self-efficacy. A revised, version of the Modified Drinking Motives Questionnaire (DMQ-R) (Grant et al., 2007) will be used to assess self-efficacy across a variety of high-risk situations. Greater self-efficacy predicts positive outcomes following alcohol treatment (Annis & Graham, 1998; Breslin et al., 2000; LaBrie et al., 2005a, 2005b, 2005c) conceptually is a key component of MI,¹⁰⁰ and is related to less alcohol use among at-risk drinkers (Walton, 2007a, 2007b)

Psychological Distress. The Generalized Anxiety Disorder 7 (GAD-7) questionnaire is used for screening and severity measuring of generalized anxiety disorder and will be used as a measure of perceived anxiety (Lowe et al., 2008).

The Post-Traumatic Disorder Checklist-Military Version (PCL-5) will be used to measure DSM-V PTSD symptoms (Weathers et al., 2013). We will also include items from the Mini-International Neuropsychiatric Interview (MINI) to assess PTSD symptoms (Sheehan et al., 1998).

Unit Risk Inventory. Items from the Unit Risk Inventory (Army Center for Substance Abuse Program, 2011), developed by the Army Substance Abuse Program are included to assess financial situation, suicidality and drinking attitudes in the military.

Healthcare Service Use. We will use the Treatment Services Review to measure health services use. It has adequate reliability and validity (French, 2000; Kaminer et al., 1998; McLellan et al., 1992). We will focus on services for the following problem areas: prescription opioid and sedative use, alcohol use, and psychiatric treatment. The timeframe will be modified to measure past 4 months service utilization.

Readiness to Change. We will also have additional questions related to the importance and confidence to change as separate components of readiness to change. We will measure with the use of visual analog rulers; these rulers have been shown to correlate with longer surveys, and to predict outcomes in alcohol intervention studies (Daepfen et al., 2007; Hesse, 2006; LaBrie et al., 2005).

Social Support. Social support will be assessed using the Deployment Risk and Resilience Inventory (DRRI) (King et al., 2006). The DRRI survey instrument is used to assess the key deployment-related factors implicated in the health and well-being of military veterans. With the nature of military deployment changing, with a larger proportion of women, National Guard and Reserves being deployed for more contemporary conflicts, the DRRI was developed to provide a more comprehensive assessment of the current combat-related experiences.

Alcohol-related consequences. The Young Adult Alcohol Consequences Questionnaire (Barry et al., 2012; Kahler et al., 2005; Tripp et al., 2015) will be used to measure consequences of alcohol

use. This measure has been used in the National Guard population.

Barrett Impulsiveness scale. Measures impulsive behaviors including behaviors related to motor control, non-planning, attention, internal stimulation, & external motivation (Patten et al., 1995).

The Conflict Tactics Scales (CTS). The Conflict Tactic Scales (Straus, 1990) is the most widely used measure of domestic violence. We will use a collapsed version of the CTS to measure partner and non-partner violence.

Dimensions of Anger Reactions. The DAR measures anger disposition directed towards others primarily measures Trait Anger. The DAR is a psychometrically strong measure, potentially useful for the evaluation of anger in PTSD (Forbes et al., 2004; Novaco & Chemtob, 2002).

Post-app assessment. The post-intervention assessment will include questions regarding importance and usefulness of the app will occur following the 12 week SP-BI.

Statistical Analysis Plan (SAP)

To minimize the likelihood of chance associations (i.e., protect against Type I errors) which can occur when multiple, unplanned analyses are conducted with large data sets, analyses for testing the main study hypotheses will be planned a priori, and will be limited to the examination of specific outcomes. In addition, analyses that are central to the purpose of the study will be clearly identified as confirmatory hypotheses, and will be clearly identified as separate from exploratory analyses. This plan of analyses is intended to outline the primary data analytic approaches that will be used to test the hypotheses for the specific aims. We will utilize an “intent-to-treat” approach in all analyses to be conservative in our estimate of intervention effects.

It is our standard practice to begin with descriptive data analyses to determine distributions of key variables, calculate transformations or collapse categories, if necessary, and review data for outliers and anomalies. Tests for linearity, independence, missingness, and distributional assumptions (e.g., normality) will also be performed. Normalizing transformations of the dependent variables will be utilized when appropriate. We will validate the randomization scheme by comparing the initial groups on key variables that could be associated with the outcomes, such as age, race, initial alcohol use severity, comorbidity, self-efficacy and stage of change. Stratified randomization should equalize the intervention groups on the key variables of gender and diagnosis of alcohol use disorder. Where we identify significant differences between groups, we will either adjust for these variables in analysis.

In general, for longitudinal analysis we will use repeated measures regression mixed effects models for continuous and non-normally distributed variables. We will use procedures SAS PROC MIXED for continuous variables and PROC GLIMMIX for dichotomous and count data (either Poisson or negative binomial), both of which allow for subject-specific inference (e.g., allows for the estimation of subject-specific effects of interventions). The selection of the covariance matrix in the PROC MIXED procedure will be determined by the distribution of the data (e.g., normally) and covariance structure. The random parameter specified will be the subject effect and we will test for random slopes and intercepts. One of the advantages of these analytic approaches is that all available data are used in the analysis, rather than case-wise

deletion if a follow-up interview is missing (see below for more detail). All analyses of the intervention and EUC condition will adjust for the two randomization stratification variables, gender and diagnosis of alcohol use disorder.

Missing data. To minimize missing data, we will make every effort to gather follow-up information for all participants. Specific strategies to retain participants that have proven successful in our prior research are described above. The use of mixed effects regression to model individual trajectories will allow the use of data from all participants (including those with incomplete follow-up data) and provides unbiased parameter estimates that account for missing data under the missing-at-random assumption.¹⁴⁸ If our examination of the pattern of missingness suggests that the missing-at-random assumption is untenable, we will handle missing data with a pattern mixture model.¹⁴⁹ Where we have missing data on individual variables that are necessary for analysis, we will impute using SAS PROC MI to perform multiple imputation of missing data and PROC MIANALYZE to combine the results of PROC MI. We have found that sometimes 5 imputations are not enough to achieve optimum results and we increase number of imputations until we see each variable having 100 degrees of freedom or more.

Power Analyses. We propose to enroll a relatively large N at baseline (750, or 375/baseline group) in order to have sufficient power to: (1) detect potentially smaller differences in outcomes of SP-BI compared to EUC as SP-BI has potential for successful implementation even if effect sizes are smaller because of the relatively low cost to maintain this technology-based intervention, and (2) have sufficient power for tests of moderators of the interventions. Longitudinal mixed effects models for binomial, count, and continuous dependent variables will be used to test the aims. We estimate power for an anticipated reduced sample size at 12 months assuming a conservative 80% follow-up (achieved in our previous studies with this population), even though our proposed mixed models use all available follow-up data.

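### Site is not pre-specified in the arm comparisons of a two-site trial: a small, cheaply recovered loss of precision and an adjustment left to a data-driven choice

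*Combined protocol and SAP*

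**What the plan says.** The combined document mentions sites once. The Design section gives the recruitment target as screening "to identify 750 participants with at-risk drinking across the 2 sites", split 375 to each arm. It does not say what the two sites are or how participants divide between them.

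Under Randomization: "Random assignment will be stratified based on gender and an AUDIT" score cut-off. Site is not a stratum.

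In the SAP's paragraph on longitudinal analysis, the covariates for the arm comparisons are stated as follows: "All analyses of the intervention and EUC condition will adjust for the two randomization stratification variables, gender and diagnosis of alcohol use disorder". The only random term is at subject level: "The random parameter specified will be the subject effect and we will test for random slopes and intercepts".

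The SAP's paragraph on descriptive analyses adds a check of the randomisation by "comparing the initial groups on key variables that could be associated with the outcomes, such as age, race, initial alcohol use severity" and further items. Site is not named, but the list is open-ended. The consequence of a finding is then given: "Where we identify significant differences between groups, we will either adjust for these variables in analysis". No alternative follows the word either, and no significance level is stated.

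**The concern.** In a trial run at more than one site, outcome levels often differ by site. Site is therefore usually a stratum, a covariate or both. Here it is neither.

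Two things are at stake. The first is precision: any stable difference between the sites stays in the variance against which the arms are compared. The second is pre-specification. The SAP opens by committing to analyses planned in advance, yet whether site is adjusted for would depend on a significance test of the observed allocation. As written, nothing in the planned output would show the treatment estimate at each site.

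**Working it through.** **Inputs from the documents.** 375 per arm, so 2 × 375 = 750. The Power Analyses section assumes 80% follow-up at 12 months: 0.80 × 375 = 300 per arm, 600 in all. The power text available gives no alpha, SD, effect size or power, so 750 cannot be re-derived and no stated power figure is contradicted.

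**Assumptions, not in the documents.** Share p of participants at one site: 0.5 (0.8 as a variant). Between-site difference d: 0.1 to 0.5 within-site SD. Two-sided alpha 0.05. Reference power 80% with site adjusted. Continuous outcome compared at one time point.

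**Step 1: reference effect.** With within-site SD 1 and n = 300 per arm, SE = √(2/300) = 0.0816. The difference detectable with 80% power is (1.960 + 0.842) × 0.0816 = 0.229 SD.

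**Step 2: where chance imbalance goes.** The arm difference in site share has variance 2p(1−p)/n. At p = 0.5 and n = 300 its 95% range is ±1.96 × √(2 × 0.25/300) = ±8.0 points. Multiplied by d = 0.5, this moves the estimate by at most about ±0.040 SD, against a standard error of 0.082 SD. The variance of the unadjusted arm difference is

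2/n + d² × 2p(1−p)/n = (2/n) × [1 + p(1−p)d²].

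The second term on the left is exactly the variance due to chance site imbalance, so the unadjusted standard error already contains it.

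**Step 3: type I error.** In a simulation with site omitted (20,000 replicates, 300 per arm, p = 0.5), the two-sided rejection rate under no effect was 4.9% at d = 0.2 and 5.2% at d = 0.5. The simulation error is about ±0.3 points (1.96 × √(0.05 × 0.95/20,000)), so both agree with the nominal 5%.

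**Step 4: precision lost.** The fraction of the standard error removed by a site term is 1 − 1/√(1 + p(1−p)d²). Power with site omitted is Φ(2.80/√(1 + p(1−p)d²) − 1.96). At p = 0.5:

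| d (SD) | Variance factor | SE removed by site term | Power, site omitted | Points lost from 80% |
|---|---|---|---|---|
| 0.1 | 1.0025 | 0.1% | 79.9% | 0.1 |
| 0.2 | 1.0100 | 0.5% | 79.6% | 0.4 |
| 0.3 | 1.0225 | 1.1% | 79.1% | 0.9 |
| 0.5 | 1.0625 | 3.0% | 77.6% | 2.4 |

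An 80/20 split costs less: at d = 0.5 the variance factor is 1.04 and power is 78.4%, a loss of 1.6 points.

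**Step 5: what the baseline check would catch.** If significant means the 5% level, then with 375 per arm and p = 0.5 it takes a difference in site share beyond about 1.96 × √(2 × 0.25/375) = 7.2 points to trigger adjustment. Smaller imbalances would leave site out of the model. The check therefore does not reliably recover the precision, and it makes the model depend on the data.

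**The case against.** A reader might infer that one arm could by chance draw more people from a heavier-drinking site, and that the resulting shift is an uncontrolled error in every comparison. The documents do not support that. Allocation is individual, so site is balanced in expectation, and Step 2 shows that the chance shift is already inside the standard error. Nor is control wholly absent. Initial alcohol severity is among the variables to be compared at baseline, an AUDIT cut-off is a stratum, and site could be checked under the open-ended list. Because site was not a stratum, leaving it out of the model also does not depart from analysing as randomised.

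A reader might also infer that the sites have different staff or deliver the intervention differently. The documents say neither. Participants are National Guard members in one state and the intervention comes through a smartphone app, which leaves less scope for differences in delivery.

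It is also fair to say that the SAP does not limit adjustment to the two named variables, and that a stable site difference would sit in between-subject variance. If baseline is part of the modelled trajectory, which is not stated, much of that difference would cancel from a contrast of change, so the losses in Step 4 could be smaller still.

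All of this stands and makes the point a minor one. It does not answer two things. No sentence commits the trial to adjusting for site, and the one route to doing so runs through a significance test after allocation is known, in a sentence that is itself incomplete.

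**Conclusion.** The omission is certain; its effect is small. Site is neither a stratum nor a pre-specified covariate or random effect. The cost is about 0.1% to 3% of the standard error, or 0.1 to 2.4 power points from 80%, for a 50/50 split, 300 per arm and a site difference of 0.1 to 0.5 SD. The upper end needs the largest assumed difference.

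The figures are for a continuous outcome. In the logistic models planned in PROC GLIMMIX, omitting site can also slightly attenuate the subject-specific effect. The statement that there is no bias concerns the comparison as randomised; the documents give no follow-up figures by site from which to judge the effect of drop-out.

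The case for change rests on small but nearly free precision and on settling the model in advance, not on any threat to validity.

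**What to change.** In the SAP's paragraph on longitudinal analysis, state what the two sites are and add site as a fixed effect to every SP-BI versus EUC model, next to the two stratification variables. Fix this before unblinding, and do not make it conditional on the baseline comparison. Report the treatment estimate by site descriptively, without a test. If the sponsor prefers to leave site out, the SAP should say why.

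The cost is one SAP sentence and one model degree of freedom, with no extra participants.

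Adding site as a third randomisation stratum (2 × 2 × 2 = 8 strata) is optional and applies only if enrolment is still open, which the documents do not show. The expected numbers of women and of participants above the AUDIT cut-off should be checked first, because the documents give neither and some strata could be sparse.

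### Covariates beyond the two stratifiers are chosen by a baseline significance test, and no outcome's own baseline value is guaranteed a place in its model

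*Combined protocol and SAP*

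**What the plan says.** The SAP opens by promising that confirmatory analyses will be specified in advance. Its second paragraph then sets out a baseline check: "We will validate the randomization scheme by comparing the initial groups on key variables that could be associated with the outcomes". The variables are given as an open list, "such as age, race, initial alcohol use severity, comorbidity, self-efficacy and stage of change". The consequence of a finding is: "Where we identify significant differences between groups, we will either adjust for these variables in analysis". No test or level is stated, and no alternative follows the word either.

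The longitudinal analysis paragraph fixes two covariates: "All analyses of the intervention and EUC condition will adjust for the two randomization stratification variables, gender and diagnosis of alcohol use disorder". On the model itself it says "we will use repeated measures regression mixed effects models for continuous and non-normally distributed variables", with a subject random effect and tests for random intercepts and slopes. It does not say whether baseline is a response visit, a covariate, or absent.

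Three other places matter:

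- Randomization: "Random assignment will be stratified based on gender and an AUDIT" score cut near 19 (the symbols are garbled in the extracted text). The SAP calls the same stratifier an alcohol use disorder diagnosis.
- Measures, Alcohol Use: "we will assess these alcohol consumption variables using counts and continuous response scales".
- Power Analyses: 375 per arm at baseline, and 12-month power "assuming a conservative 80% follow-up".

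**The concern.** After proper randomisation, a significant baseline difference is a chance event. It carries no information on how strongly the variable predicts outcome, which is the reason to adjust. The trigger has three consequences:

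- **Prespecification.** The covariate set of the confirmatory models is not known until the baseline data have been tested.
- **Precision.** Baseline drinking is likely to be among the best predictors of later drinking. Under the rule it enters through the trigger in only about 1 trial in 20 (at a 0.05 level).
- **Uncorrected imbalance.** A baseline difference that narrowly misses the threshold is left alone, although it shifts the estimate almost as much as one that just passes.

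The second of these bears directly on this trial. The Power Analyses section justifies enrolling 750 by the wish to detect smaller effects and to test moderators, and the rule gives up precision needed for both.

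**Working it through.** **Inputs from the documents.** 375 per arm with 80% followed at 12 months gives 375 × 0.80 = 300 per arm. Six variables are named in the baseline check. The supplied text gives no alpha, power, effect size or SD, so there is no plan figure to reproduce beyond 2 × 375 = 750.

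**Assumptions.** Two-sided 0.05; continuous outcome with unit SD; baseline to follow-up correlation r = 0.3, 0.5 or 0.7. These are not in the documents.

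**1. How often the rule fires by chance.** With six independent tests, 1 − 0.95^6 = 26%. At a 0.10 level, 1 − 0.90^6 = 47%. Correlated variables would give less.

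**2. Variance of the treatment contrast at one follow-up visit.** Relative to a follow-up-only model (variance 1), baseline as a covariate gives 1 − r², and unconstrained change from baseline gives 2(1 − r). Baseline as a response with equal arm means (four visits, compound symmetry) gives the same as the covariate model.

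| | r = 0.3 | r = 0.5 | r = 0.7 |
|---|---|---|---|
| Baseline as covariate | 0.91 | 0.75 | 0.51 |
| Unconstrained change | 1.40 | 1.00 | 0.60 |
| Cut versus follow-up only | 9% | 25% | 49% |
| Cut versus unconstrained change | 35% | 25% | 15% |
| Cut versus baseline as response, equal arm means | 0% | 0% | 0% |

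**3. Allowing for the severity stratum, which is always in the model.** Suppose the stratum is a cut on the same normal measure, with a proportion p of participants above it. It then explains q = φ(z_p)²/[p(1 − p)] of baseline variance: 0.342 at p = 0.10 and 0.490 at p = 0.20 (both assumed). The remaining cut versus follow-up only is r²(1 − q)/(1 − r²q): 5–6%, 15–18% and 33–39% at r = 0.3, 0.5 and 0.7.

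**4. Detectable effect at 80% power, r = 0.5.** 2.80 × √(2/300) × √(1 − r²q) = 0.229, 0.219 and 0.214 SD for q = 0, 0.342 and 0.490. With baseline in the model it is 2.80 × √(2/300) × √0.75 = 0.198 SD.

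**5. Power for a 0.20 SD effect** (simulated z-statistics; adjust only if baseline p < 0.05).

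| | r = 0.3 | r = 0.5 | r = 0.7 |
|---|---|---|---|
| Significance rule, no stratum effect | 69% | 70% | 71% |
| Always adjusting | 73% | 81% | 93% |

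With the stratum effect at r = 0.5, the rule gives 73% (q = 0.342) or 75% (q = 0.490).

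**6. Overall type I error of the rule.** Write z for the unadjusted test statistic and z_b for the baseline one. The adjusted statistic is independent of z_b, so the error is 0.05 − P(|z| > 1.96 and |z_b| > 1.96) + 0.05². At r = 0.3, 0.5 and 0.7 this is:

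- 0.05 − 0.0049 + 0.0025 = 4.8%
- 0.05 − 0.0093 + 0.0025 = 4.3%
- 0.05 − 0.0165 + 0.0025 = 3.6%

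**7. Type I error given the imbalance that occurred, r = 0.5.** Below the trigger, z given z_b is N(r·z_b, 1 − r²). The error is 2.4% at z_b = 0, 8.2% at 1.5 and 12.2% at 1.9. With the stratum effect it is 3.0–3.4%, 7.0–7.4% and 9.3–10.2%.

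**8. Counts.** An illustrative Poisson-lognormal simulation used log-SD 1, mean 4 or 8, 600 participants and 1,000 trials. It fitted negative binomial models with and without log(1 + baseline), follow-up only and without a stratum. Variance cuts were 14–19%, 39–45% and 57–65% at log-count correlations of about 0.3, 0.5 and 0.7. Binary outcomes were not computed.

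**The case against.** **The plan may already use baseline.** This is the strongest reply. The SAP models individual trajectories and intends to use participants with incomplete follow-up; someone with no follow-up visit contributes only if baseline is a response. If baseline is a response and arm means are constrained equal, nothing is lost. This stands as a limit on size: the loss runs from 0% upward. It does not settle the matter, because the constraint is nowhere stated, and without it a comparison of change loses 15–35%.

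**The model borrows strength across visits.** Correct, but the effect is small. Assume compound symmetry, r = 0.5, 375 per arm at months 4 and 8, and 300 at month 12. The variance cut is then 22% rather than 25%, the detectable effect falls from 0.221 to 0.195 SD, and power for 0.20 SD is 72% without baseline against 82% with it.

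**The conditional errors treat the baseline and outcome samples as the same.** They do. If the baseline test uses 375 per arm, the outcome test 300, and dropout is random, the correlation between the two statistics is 0.5 × √(300/375) = 0.447. The error at z_b = 1.9 is then 10.8% rather than 12.2%, and at z_b = 0 it is 2.8% rather than 2.4%. The pattern is unchanged.

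**The candidate variables were picked as plausibly prognostic.** True of the pool. The choice from within it is still made by chance imbalance.

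**Adding baseline to a logistic model changes the effect being estimated.** This has little force here, since the SAP already aims at subject-specific inference through PROC GLIMMIX.

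The incomplete sentence may be a slip or lost text, and nothing here depends on it.

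**Conclusion.** The concern holds. The plan states a rule that selects covariates by baseline significance, and it does not guarantee that any outcome's own baseline value is in the model. The always-included severity stratum is a coarse split on alcohol severity; it does not replace baseline binge drinking, drug use or depressive symptoms.

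The consequence is loss of precision and of prespecification, with no inflation of overall type I error and no average bias. On a follow-up-only reading with r = 0.5, the rule costs about 6 to 11 percentage points of power for a 0.20 SD effect (75% or 70% against 81%). At r = 0.3 the gain from always adjusting is modest (a 5–9% variance cut), and if baseline is a constrained response it is nil. The reading of the text is secure. The size rests on assumed correlations, an assumed stratum share, a 0.05 trigger and a continuous outcome. It should be corrected, since the better rule needs no new data.

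**What to change.** 1. Delete the rule that makes adjustment depend on a significant baseline difference.
2. State that every outcome model adjusts for gender, the severity stratum exactly as used in the randomisation system, and the participant's own baseline value of that outcome. Say which form applies: a covariate, or a response visit with arm means constrained equal. For count outcomes, state the scale on which baseline enters.
3. First reconcile the stratifier's definition: the Randomization section uses an AUDIT score cut, while the SAP refers to an alcohol use disorder diagnosis.
4. Keep the baseline comparison as a descriptive table without p-values.
5. Label any further covariate adjustment as a sensitivity analysis, with its variables listed in advance.

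The cost is SAP wording only. The Randomization section places the baseline assessment before assignment, so the values are already collected; sample size and procedures do not change.
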